		12.2.6 Monitoring Serious Adverse Events	
		12.2.7 Follow-up of Serious Adverse Events	36
13	Stud	ly Training	36
13		Study Training	36
	13.1	Study Hammig	50
14		ulatory Considerations	37
		Health Insurance Portability and Accountability Act	37
		Inclusion of Women and Minorities	37
		ClinicalTrials.gov Requirements	37
		Retention of Records	37
	14.5	Public Use Data Set	38
15	Bibli	iography	38

List of Tables

1	Representative comments from family, hospitalist, and PCP focus groups	10
2	Results of the BeneFIT RCT	11
3	RCTs that suggest efforts to augment follow-up can potentially result in overtreatment	12
4	Selection of outcomes informed by focus groups	14
5	Secondary, exploratory, and safety outcomes	16
6	Study Population	19
7	Study Schedule	22

1 Study Summary

Title	The Follow-up Automatically vs. As-Needed		
	Comparison (FAAN-C) trial		
Short Title	FAAN-C (pronounced "fancy")		
Design	FAAN-C is a multicenter randomized		
	controlled trial that will enroll 2,674 patients		
	across participating hospitals		
Study Duration	5 years		
Data Coordinating Center	University of Utah		
Primary objectives	Compare the effectiveness of as-needed vs.		
	automatic post-hospitalization follow-up		
Number of Subjects	2,674 patients		
Eligibility Criteria	Children, hospitalized for pneumonia, skin and		
	soft tissue infection, acute gastroenteritis, or		
	urinary tract infection will be eligible for		
	enrollment.		
	Excluded: Children with a history of comorbid		
	disease that is both chronic and complex		
Statistical Methodology	Analyses will be conducted in an		
	intention-to-treat (ITT) manner, in which all		
	randomized subjects are included and analyzed		
	according to their randomization assignment.		

2 Background and Rationale

2.1 Background

Follow-up visits are common A "follow-up visit" occurs when a medical provider instructs a patient to schedule an additional medical visit for the purpose of re-evaluating the patient's condition in the future. Follow-up visits are utilized in nearly every clinical setting, including follow-up after acute visits to primary care, urgent care, specialty care, the emergency department, or the hospital. Nationally representative survey data from the 2018 Medical Expenditure Panel Survey demonstrate that US children attend nearly 20 million follow-up visits annually, at a cost of \$4.3 billion.¹

Automatic post-hospitalization follow-up has intuitive appeal The present proposal focuses on one type of pediatric follow-up visit: the post-hospitalization follow-up visit. Most hospitalized patients (>80%) are prescribed automatic post-hospitalization follow-up, meaning they are routinely instructed to visit their primary care provider (PCP) shortly after hospital discharge, regardless of

symptom improvement.^{2, 3} The majority of patients comply with these instructions and attend the follow-up visit.^{3–5} The intuitive appeal of automatic follow-up is to provide an opportunity for PCPs to connect with patients and their families to: verify that a patient is following an expected course, adjust the treatment regimen if needed, provide additional reassurance about the patient's illness, and address any gaps in continuity of care (e.g., immunizations). Automatic follow-up is especially intuitive for children with chronic and/or complex medical needs, who are at increased risk for adverse events^{6, 7} and readmission.^{8–11} For this reason, discharge improvement interventions that include automatic follow-up have focused on populations of children with chronic and/or complex medical needs, such as children hospitalized for asthma, ¹² premature birth, ^{13, 14} or major surgery. ¹⁵

Automatic follow-up for previously healthy children recovering from common infections may not be necessary While the rationale for automatic follow-up is compelling for children who have chronic and complex medical needs, most hospitalized children are previously healthy and hospitalized for acute conditions from which complete recovery is expected. ^{16, 17} Five of the top 10 reasons for pediatric hospitalization are acute infections, including: pneumonia, bronchiolitis, skin and soft tissue infections, gastrointestinal infections, and urinary tract infections. ¹⁸ Together, these infections are responsible for over 500,000 pediatric hospitalizations each year in the US. ¹⁸ After hospital discharge, the vast majority of previously healthy children recover from these infections within a matter of days and rarely experience an interim worsening of their illness (readmission rates are <5% ¹⁰). Given such a reassuring prognosis, the benefit of automatic follow-up for previously healthy children recovering from common infections is unclear.

PRN follow-up is a patient and family-centered alternative to automatic follow-up Patient and family-centered care means that patient and family values guide all clinical decisions. Patients and families whose preferences are incorporated into their plan of care make more value-congruent choices and are more likely to follow the plan of care. A PRN (*pro re nata*, "as-needed") follow-up strategy is aligned with the principles of patient and family-centered care, encouraging families to monitor their child's symptoms after hospital discharge and schedule a visit if the child does not improve or if new concerns arise. As such, PRN follow-up empowers families with greater autonomy and allows them to consider their preferences and values when deciding whether or not to pursue post-hospitalization follow-up. Taking this decision-making away from families runs the risk of undermining their sense of self-efficacy—a patient's or parent's confidence to solve self-identified problems. Despite being patient and family-centered, PRN follow-up is prescribed to a minority of patients (10–15%) largely because of limited evidence. PRN follow-up

Preliminary data Families and medical providers struggle, not knowing which follow-up option is best. To better understand the perspectives of end users of post-hospitalization follow-up, we conducted three separate focus groups (Table 1), among: 1) parents of children who had been hospitalized, 2) hospitalists (physicians who care for hospitalized children), and 3) PCPs. Focus groups consisted of 6–8 participants each. Participants in each focus group came from at least 3 different FAAN-C institutions. Overall, families felt that their circumstances and the options available to them were not adequately considered in post-hospitalization follow-up decision-making.

Hospitalists expressed uncertainty about the available evidence to help guide their recommendations. PCPs saw advantages to some follow-up visits, but worried that others were unnecessary. The unifying theme for end-users was the need for better evidence to guide conversations and decision-making around follow-up.

Table 1: Representative comments from family, hospitalist, and PCP focus groups

Focus group question	Representative participant comments
For families: What has been your	"They tell you to go visit the doctor but they have no idea
experience with follow-up care	if you have transportation, money for gas, money for
instructions after your child's	parking, help with child care"
hospitalization?	"Whatever option they give you, you think that's all there
	is"
For hospitalists: Please describe	"It's a historical norm [automatic follow-up], that gives us
your decision-making for	some reassurance, but it's never been evidence tested"
post-hospitalization follow-up "We normally do this [automatic follow-up], we	
recommendations to families.	have done it, but it isn't backed in any confidence or any
	evidence"
For PCPs: Please describe your	"For anxious families or families with unanswered
experience with	questions it's been helpful"
post-hospitalization follow-up	"I feel bad when they're in clinic and they look great, and I
visits.	say ok you're better, sorry you have to pay a copay"
	"Our schedules are really packed full and you hate to have
	a family come in if they don't really need to be there"

BeneFIT RCT demonstrates promise of PRN follow-up for one common pediatric infection. Our team completed an RCT comparing PRN vs. automatic follow-up, called the Bronchiolitis Follow-up Intervention Trial (BeneFIT).²³ BeneFIT was a multicenter trial conducted across 4 hospitals. Bene-FIT participants were 304 children hospitalized for a common infection called bronchiolitis. Results from BeneFIT are presented in Table 2. Four-fold fewer families attended post-hospitalization follow-up visits in the PRN group (19%) compared to the automatic group (81%). Both groups otherwise had similar outcomes, including no significant differences in parent anxiety, symptom duration, or readmission.

Outcome	PRN N = 138	Automatic N = 131	Absolute Difference (95% CI)
Attendance of a follow-up visit, n (%)	26 (19)	106 (81)	-63 (-53 to -72)
Parent anxiety score, a mean	3.9	4.2	-0.3 (-1.0 to 0.7)
Days to symptom resolution, mean	10	11	-1 (-3 to 1)
Readmission, n (%)	3 (2)	5 (4)	-2 (-6 to 2)

Table 2: Results of the BeneFIT RCT

2.2 Rationale

The importance of examining post-hospitalization follow-up Observational studies have reached conflicting conclusions about post-hospitalization follow-up, with some studies finding an association between automatic follow-up and decreased rates of hospital revisit^{25–31} and other studies finding no association or increased rates of hospital revisit. 32-37 BeneFIT remains one of the only pediatric RCT to examine patient and family-centered outcomes for post-hospitalization follow-up.²³ Generalizations about post-hospitalization follow-up after BeneFIT are limited because BeneFIT was not powered to detect differences in hospital readmission, and BeneFIT only enrolled children with one specific type of infection, bronchiolitis. A systematic review of hospital discharge interventions highlighted post-hospitalization follow-up as its first "Persistent Literature Gap." 38 A national collaboration sponsored by the American Academy of Pediatrics' Quality Improvement Innovation Networks and the Section on Hospital Medicine concluded that certain quality measures, including post-hospitalization follow-up, "require further study for feasibility, measurement reliability and validity, and effectiveness in preventing harm."³⁹ Despite substantial gaps in the literature, multiple quality metrics have been developed recently to promote automatic post-hospitalization follow-up, including Pedi-BOOST, the Center of Excellence on Quality of Care Measures for Children with Complex Needs, and the Pediatric Transition Experience Measure. 40-43 Hospitals are adopting these measures and promoting automatic post-hospitalization follow-up.^{4,5}

PRN follow-up has potential to improve delivery of care High-value care makes efficient use of resources and ensures that patients receive meaningful benefit.⁴⁴ The "Triple Aim" in high-value care is to simultaneously improve the patient experience of care, reduce the cost of care, and improve the health of populations.⁴⁵ PRN follow-up has the potential to achieve this status by decreasing the amount of time that patients spend seeking medical care, decreasing patient costs, and decreasing exposure to unnecessary medical tests and treatments.

1) Time and cost-savings. Clinic visits require an average of two hours of a family's time and result in out-of-pocket expenses and lost income. 46 Out-of-pocket expenses include money for travel, parking, co-pays, and child care. These burdens disproportionately affect racial/ethnic minority and lower income families. For example, attendance of a clinic visit requires 30% more time

^aPrimary outcome, scored by validated instrument;²⁴ higher scores= greater anxiety

for Hispanic and Non-Hispanic Black families compared to Non-Hispanic white families due to increased travel and in-clinic time.⁴⁷ Out-of-pocket healthcare expenditures relative to income are >300% higher for families whose income is less than the Federal Poverty Level, compared to high-income families.⁴⁸ Lost income occurs when parents take time away from work to attend the visit, which is particularly challenging for parents who may have already taken time away from work during their child's hospitalization. Lost income at the time of hospitalization is highest for racial minority and single-parent households.⁴⁹ PRN follow-up could mitigate these burdens without compromising quality of care.

2) Decreased exposure to unnecessary medical tests and treatments. Seemingly benign medical interventions have the potential to precipitate additional tests and interventions that are unnecessary, costly, and potentially harmful.^{50–52} Four recent pediatric RCTs have compared PRN follow-up or usual care to an intervention that augments follow-up (Table 3). In each RCT, augmented follow-up resulted in more medical care, without otherwise improving patient outcomes. A pattern of increased medical care that does not improve patient outcomes is concerning for overtreatment.⁵³ For children recovering as expected, avoidance of a post-hospitalization follow-up visit might reduce exposure to overtreatment.

Table 3: RCTs that suggest efforts to augment follow-up can potentially result in overtreatment

RCT	Population	More intensive follow-up group	Less intensive follow-up group	Primary Outcome	Potential Overtreatment
Auger et al ⁵⁴	Hospitalized children (variety of diagnoses)	Post- discharge nurse-led home visit	No home visit	30-day reutilization rate for urgent health care services	The 30-day reutilization rate was higher in the augmented follow-up group.
Auger et al ⁵⁵	Hospitalized children (variety of diagnoses)	A post- discharge telephone call	No phone call	30-day reutilization rate for urgent health care services	No significant difference, but point estimate for the 30-day reutilization rate higher in augmented follow-up group.
Colaco et al ⁵⁶	Children with distal radius buckle fractures	Automatic PCP follow-up	PRN follow-up	Parent report of child's physical function 3 weeks after injury	No difference in primary outcome; more physician visits, higher costs, and more radiographs for augmented follow-up.
[name] et al ²³ (BeneFIT)	Hospitalized children with bronchiolitis	Automatic PCP follow-up	PRN follow-up	Parental anxiety 7 days after discharge	No difference in primary outcome; new prescriptions at follow-up visits for therapies discouraged by national guidelines. ⁵⁷

3 Objectives and Outcomes

3.1 Primary Objective

The primary objective of this study is to compare the effect of a recommendation for PRN vs. automatic post-hospitalization follow-up on hospital readmission within 14 days of hospital discharge. We hypothesize that a recommendation for PRN follow-up will be non-inferior to a recommendation for automatic follow-up in terms of hospital readmission rates.

3.2 Secondary Objectives

Our secondary objectives are to determine the effect of a recommendation for PRN follow-up, compared to a recommendation for automatic follow-up, on:

- medical interventions that a child receives after hospital discharge
- child health-related quality of life

3.3 Study Process Measure

The proportion of participants who attend a follow-up visit (in-person or via telehealth) within 7 days of hospital discharge will be reported but will not be categorized as a formal outcome. Rather, the proportion of participants who attend a post-hospitalization follow-up visit will be a study process measure. A prior trial demonstrated that randomization to a recommendation of PRN vs automatic follow-up does result in a large difference in follow-up visit attendance.²³ We hypothesize that recommendations for PRN vs automatic follow-up in FAAN-C will similarly result in large differences in follow-up visit attendance.

4 Study Outcomes

4.1 Selection of Outcomes

Selection of study outcomes was informed by the previously described focus groups involving parents of hospitalized children, hospitalists, and PCPs. Illustrative quotes that influenced selection of specific outcomes are presented in Table 4. Parents, PCPs, and hospitalists were clear that hospital readmission should be the primary outcome.

Page 14 of 44 Protocol 1.00 ([name])

Table 4: Selection of outcomes informed by focus groups

Participant	Representative participant responses to a question asking which outcomes would be important to study	Outcome added to FAAN-C
Parent	"The impact on parents, their time away from work"	Parent time
Parent	"We're all very invested in making sure things work out the best for our kids, often at the expense of our own health. Anxiety would be interesting to see because that plays into the situation and comes back to impact our kids as well."	Parent anxiety
Parent	"The one that really stands out to me is the number of times we have to go back to the hospital after being sent home."	Hospital readmission as the primary outcome
PCPs	"I feel like I develop my relationship with my patients and families through their well-child check-ups, not the sick or hospital follow-up appointments."	Well-child visits
PCPs	"I like to at least call my patients and parents after they are discharged from the hospital to maintain that relationship."	Telephone and electronic communications with medical providers
PCPs	"We worry that if kids don't follow-up, are they going to get so bad they need to be readmitted, so we hope that the follow-up prevents readmission."	Hospital readmission as the primary outcome
Hospitalist	"I think it helps to strengthen the relationship between the PCP and the family, so that they can see their PCP as not just the well doctor, but the well and sick doctor."	Usual place of medical care
Hospitalist	"I would look at health outcomes, readmission number one and emergency department utilization."	Hospital readmission as the primary outcome; total additional ambulatory visits

4.2 Primary Outcome

The primary outcome is the proportion of participants who experience a hospital readmission within 14 days of their index hospital discharge. All causes of hospital readmission, even if seemingly unrelated to the index infection, will be scored as a hospital readmission for the purpose of the primary outcome. Hospital readmission will be measured primarily by parent report. On days 7, 14, and 30 after hospital discharge, parents will be surveyed and asked about hospital readmissions since discharge. Parent report allows capture of readmissions that occur outside of a given hospital's electronic health record (EHR) system. However, parent report may be inaccurate for a proportion of participants and will be missing for others. Parent report will be assumed inaccurate in two cases: (1) a parent reports a readmission at a hospital whose records are available in the EHR, but there is no readmission documented in the EHR. These cases will not be counted as readmissions. (2) Cases in which a parent reports no readmission but there is a readmission documented in the EHR. These cases will be counted as readmissions when parent report is missing, imputation will be utilized, as described in the missing data section.

4.3 Secondary Outcomes

Medical interventions and child health-related quality of life are pre-specified as the main secondary outcomes under consideration. Medical interventions are a main secondary outcome because decreasing exposure to unnecessary medical tests and treatments is a core component of improving healthcare value and a potential advantage of PRN follow-up. Medical interventions will be measured by parent report. Child health-related quality of life is a main secondary outcome because it is a patient-centered measure of how much a child's health is impacting their usual activities or routines. Child health-related quality of life will be measured by child report, unless the child is too young to self-report or prefers parent report.

4.4 Exploratory Outcomes

Exploratory outcomes are listed in Table 5. If participants in the PRN follow-up group are able to attend fewer post-hospitalization follow-up visits, the cost burden to parents, the child's time away from school or daycare, and parent time away from work and other responsibilities might be lower. We hypothesize that a recommendation for PRN follow-up might result in greater telephone and electronic communications between families and the child's medical providers. It is possible that a recommendation for PRN follow-up could serve as a missed opportunity to reconnect a child and their primary care provider, resulting in small decreases in well-child visits, immunizations, participants who report having a usual place of medical care, and medical interventions related to the index infection. We hypothesize that the remainder of the exploratory outcomes (symptom duration, parent self-efficacy, parent anxiety, and satisfaction with care) will be similar between participants randomized to a recommendation for PRN follow-up compared to participants randomized to a recommendation for automatic follow-up. All exploratory outcomes are measured by parent report, from the time of hospital discharge until the specified time after discharge.

4.5 Safety Outcomes

Safety outcomes are also listed in Table 5. Safety outcomes were selected with the goal of capturing adverse consequences (beyond hospital readmission, the primary outcome) that families might experience as a result of a recommendation for PRN follow-up, compared to a recommendation for automatic follow-up. A recommendation for PRN follow-up may result in those participants having to attend a greater number of other types of ambulatory visits (e.g., emergency department visits). The subset of non-primary care ambulatory visits will be measured because these visits have the potential to be more burdensome for participants (i.e., larger co-pays and urgent, less convenient visits), relative to a primary care visit. It is also possible that a recommendation for PRN follow-up could result in greater exposure to medical errors after hospital discharge (e.g., medication problems, complications of care), since another medical provider may not connect with the child and family shortly after hospital discharge. In addition to the primary outcome of all-cause hospital readmission, an additional safety outcome will be hospital readmissions related to the index infection. All safety outcomes are measured by parent report, from the time of hospital discharge

until the specified time after discharge.

Table 5: Secondary, exploratory, and safety outcomes

Outcome	Definition	Expected outcomes type for analysis ^a
	Secondary outcomes	
Medical interventions	Proportion of participants who receive either a laboratory test, imaging test ^b , or a new medication within 14 days of hospital discharge	Binary
Child health-related quality of life	Mean health-related quality of life score 7 days after hospital discharge, measured by the Impact on Activities and Routines instrument	Normal
	Exploratory outcomes	
Cost burden	Mean total costs to parents (missed income and expenses) related to the participant's illness within 14 days of hospital discharge, measured by the cost burden survey in Chang et al ⁴⁹	Binomial- Gamma hurdle
Child time	Mean number of hours of school or daycare missed by the participant within 14 days of hospital discharge as a result of their medical needs	Over-dispersed Binomial
Parent time	Mean number of hours spent away from responsibilities (work or non-work related) by parents within 14 days of hospital discharge as a result of their child's medical needs	Normal or Gamma
Symptom duration	Proportion of participants who have completely recovered from their infection at 7 days after hospital discharge	Binary
Total additional ambulatory visits	Mean number of ambulatory visits (in-person or via telehealth) that a participant attends, apart from the post-hospitalization follow-up visit, within 30 days of hospital discharge; Ambulatory visits include clinic, urgent care, and emergency department (not resulting in hospital admission) visits.	Negative Binomial
Non-primary care ambulatory visits	Mean number of ambulatory visits (in-person or via telehealth) to non-primary care providers, within 30 days of hospital discharge; Non-primary care providers will include all providers outside of the clinic that families identify as their primary care clinic.	Negative Binomial
Parent self-efficacy	Mean self-efficacy score 7 days after hospital discharge, measured by the PROMIS self-efficacy short form ⁵⁸	Normal
Parent anxiety	Mean anxiety score 7 days after hospital discharge, measured by the PROMIS anxiety short form ⁵⁸	Normal or Gamma
Satisfaction with care	Proportion of participants who report agreeing or strongly agreeing with the statement, "I am satisfied with the medical care my child has received since hospital discharge," 7 days after hospital discharge	Binary
Telephone and electronic communications with medical providers	Mean number of telephone and electronic (excluding telehealth visits) communications with a medical provider within 14 days of hospital discharge	Negative Binomial
Well-child visits	Proportion of participants who attend a well-child visit within 6 months of hospital discharge	Binary
Immunizations	Proportion of participants who receive an immunization within 6 months of hospital discharge	Binary

Usual place of medical care	Proportion of participants who report having a usual place of medical care 6 months after hospital discharge	Binary	
Medical interventions related to the index infection	Proportion of participants who receive either a laboratory test, imaging ^b test, or a new medication related to the index infection within 14 days of hospital discharge	Binary	
Safety outcomes			
Medical errors	Proportion of parents who report that their child experienced a medical error within 14 days of hospital discharge, measured by the Family Safety Interview ⁵⁹	Binary	
Hospital readmissions related to the index infection	Proportion of participants who experience a hospital readmission related to the index infection within 14 days of hospital discharge	Binary	

^aOutcome type designations, particular as normal or gamma, are preliminary and may be updated based on the observed skewness in the outcome variables.

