6.1 Treatment of Subjects

At the time of hospital discharge, families will be randomly assigned to either PRN or automatic follow-up recommendations as described below:

PRN follow-up: "You do not need to schedule a follow-up visit with your child's regular doctor today. If your child's illness continues to improve, you do not need to have a visit with your child's regular doctor within the next 7 days. If your child's illness does not seem to be getting better or you develop any new concerns, we recommend that you contact your child's regular doctor to discuss whether a follow-up visit might be necessary."

Automatic follow-up: "Please schedule a follow-up visit with your child's regular doctor before leaving the hospital. Please schedule the visit to occur within the next 7 days and plan to attend the visit even if your child's illness is getting better."

The automatic follow-up instructions are aligned with proposed quality metrics⁴⁰ and previous studies of automatic follow-up.^{25, 26, 28, 32, 34} Both the PRN and automatic follow-up instructions were utilized successfully for our prior trial, BeneFIT.²³

Pragmatic features of comparators. Pragmatic features that will make findings from FAAN-C more generalizable and quickly scalable include the following: 1) Follow-up visits, whether automatic or deemed necessary in the PRN group, can be conducted either in-person or via telehealth. The decision about whether a visit should occur in person or via telehealth will be at the discretion of families and their medical providers. 2) Beyond randomization to either PRN or automatic post-hospitalization follow-up recommendations, FAAN-C is not otherwise prescriptive for a participant's medical care. Hospitalists have complete autonomy about the patient's care while hospitalized, and PCPs have complete autonomy for the patient's care after hospitalization. 3) Beyond embedding follow-up instructions in the electronic health record, the discharge process is otherwise preserved according to each hospital's usual procedures.

7 Treatment Assignment Procedures

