8.1 Study Schedule

A schedule of study events for each participant is outlined in Table 7. "While hospitalized" events will occur between the time of hospital admission and the time of hospital discharge.

Page 22 of 44 Protocol 1.00 ([name])

Table 7: Study Schedule

	While hos- pitalized	After hospital discharge			
		Day 7	Day 14	Day 30	Day 180
Screening	/				
Informed consent	/				
Parent interview	/				
Randomization	/				
Notify family, PCP, and inpatient team of assignment	/				
Chart review				/	
Process measure					 
Completion of a post-hospitalization follow-up		×			
Outcomes					
All-cause hospital readmissions		0	×	0	
Medical interventions		0	×	0	
Child health-related quality of life	0	×	0	0	
Cost burden		0	×	0	
Child time		0	×	0	
Parent time		0	×	0	
Symptom duration	0	×	0	0	
Total additional ambulatory visits		0	0	×	
Non-primary care ambulatory visits		0	0	×	
Parent self-efficacy	0	×		0	0
Parent anxiety	0	×		0	
Satisfaction with care	0	×			
Telephone or electronic communications with medical providers		0	×	0	
Well-child visits	0				×
Immunizations	0				×
Usual place of medical care	0				×
Medical interventions related to the index infection		0	×	0	
Medical errors		0	×	0	
Hospital readmissions related to the index infection		0	×	0	

^{/ =} task performed at the specified timepoint

^{○ =} measured at the specified timepoint

X = measured at the specified timepoint and this is the timepoint used for primary analyses

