8.6 Outcome Measurement

Outcomes will be measured according to the timing in Table 7. "While hospitalized" outcomes will be measured prior to randomization. "After hospital discharge" outcomes will be measured by surveying parents on days 7, 14, 30, and 180, as specified. An additional 4 days will be permitted for the collection of data on the 7, 14, and 30 day timepoints and \pm 7 days for the day 180 timepoint. For example, day 7 outcomes can be collected between day 7 and day 11. These intervals allow for holidays, weekends, and other reasons for parent unavailability that may preclude contact on the exact day.

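### The day-7 satisfaction item asks about care received since discharge, which means something different in each arm, so this exploratory comparison cannot be cleanly interpreted

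*Protocol*

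**What the plan says.** Table 5 (Protocol section 4.5) lists satisfaction with care as a binary exploratory outcome at 7 days: "Proportion of participants who report agreeing or strongly agreeing with the statement", the statement being "I am satisfied with the medical care my child has received since hospital discharge". Section 8.6 sets the survey window: "day 7 outcomes can be collected between day 7 and day 11".

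The two arms are told different things about that same period. In section 6.1 the PRN script tells families of improving children that "you do not need to have a visit with your child's regular doctor within the next 7 days". The automatic script asks for a visit in those 7 days even if the child is improving. Section 3.3 expects that the recommendations "will similarly result in large differences in follow-up visit attendance". Section 2.1 reports attendance of 19% (PRN) and 81% (automatic) in the earlier bronchiolitis trial.

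Section 4.4 predicts similar satisfaction in the two arms. Section 9.2 leaves the outcome outside the multiplicity procedure, and section 9.5 expresses binary exploratory outcomes as risk ratios.

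Table 7 (section 8.1) marks "Satisfaction with care" at two times: while hospitalized, and at day 7, the analysis timepoint. Section 8.6 places the while-hospitalized measurements before randomization.

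**The concern.** The item presupposes that the child has received medical care since discharge. Most automatic-arm families are likely to have a follow-up visit to rate by day 7. Most PRN families whose child is improving are likely to have none, because they followed the advice they were given. Some will have had other contact and some no contact at all. The latter must disagree, choose a neutral answer, leave the item blank, or agree in the sense that they are content that no care was needed. These answers mean different things, and the families who must choose among them are concentrated in one arm.

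The protocol argues for PRN follow-up partly on how families experience care (section 2.2), and this item is a direct measure of that. As worded, a lower proportion under PRN could reflect dissatisfaction or a question that did not apply. Equal proportions could hide either. An analysis plan can set scoring rules, but it cannot recover what a parent meant by an answer to a question already asked.

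**Working it through.** **Attendance, from Table 2 of the protocol.** PRN: 26/138 = 18.8%, printed as 19%. Automatic: 106/131 = 80.9%, printed as 81%. Families without a follow-up visit: about 81% (PRN) and 19% (automatic). The protocol gives no attendance figure for the present trial and none for satisfaction.

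**Model.** Let v be the proportion agreeing among families with a follow-up visit and x the proportion among those without. Both are assumed equal in the two arms, and neither is in the protocol.

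- PRN = 0.19v + 0.81x
- Automatic = 0.81v + 0.19x
- PRN minus automatic = (0.19 - 0.81)(v - x) = -0.62(v - x)

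With v = 90% (assumption):

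| x (assumed) | PRN | Automatic | Difference, points | Risk ratio |
|---|---|---|---|---|
| 95% | 94.05% | 90.95% | +3.1 | 0.9405/0.9095 = 1.03 |
| 90% | 90.0% | 90.0% | 0 | 1.00 |
| 85% | 85.95% | 89.05% | -3.1 | 0.8595/0.8905 = 0.97 |
| 80% | 81.9% | 88.1% | -6.2 | 0.819/0.881 = 0.93 |
| 70% | 73.8% | 86.2% | -12.4 | 0.738/0.862 = 0.86 |

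The sign depends only on whether x is below or above v.

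**Would such differences be noticed?** Section 9.9 randomizes 1,337 per arm with 15% attrition for the primary outcome. Applying the same attrition here (assumption), 1,337 x 0.85 = 1,136 per arm. At 2-sided 0.05, a true difference of -6.2 points would be significant with probability about 99%, -3.1 points about 61%, and +3.1 points about 80%. The trial is large enough for a wording effect of a few points to look like a finding.

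**If families without a visit left the item blank.** Respondents would number about 1,136 x 0.19 = 216 (PRN) and 1,136 x 0.81 = 920 (automatic). Missingness would depend strongly on arm. The multiple imputation of section 9.8 would then supply satisfaction with care for some children who had received none. This is the extreme case, because some families without a follow-up visit will have had other contact.

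**Table 7.** An item about the time since discharge cannot be answered before randomization, when the child is still in hospital. Section 4.4 also says that exploratory outcomes are measured from discharge onward. These places do not agree. No result changes, because day 7 is the analysis timepoint.

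**The case against.** A reader might infer that the item simply measures having had a visit and therefore biases the comparison against PRN. The protocol does not support that, for four reasons.

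- **Care is wider than the follow-up visit.** The PRN script tells families to contact the regular doctor if concerns arise. Section 4.4 expects possibly more telephone and electronic contact under PRN, and Table 5 counts other ambulatory visits separately. A parent content that no visit was needed may also agree.
- **The direction is not established.** It rests wholly on the assumed x: the difference is zero at 90% and favours PRN at 95%.
- **Some of any gap may be real.** The objective (section 3.1) is the effect of the recommendation, analysed by intention to treat. If families advised against a routine visit are less satisfied as a result, that is an effect of the recommendation. Only answers given because the item does not apply are artefact, and the item cannot separate the two.
- **The attendance figures come from another population.** Bronchiolitis is not one of the four infections enrolled. Section 3.3 commits only to a large difference.

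It is also fair that Table 5 defines only who counts as satisfied. It gives no rule for a not-applicable answer, so one should not say that the plan scores such families as dissatisfied. Response coding may sit in a survey form or analysis plan that is not shown, and its absence from the protocol is not counted here. The baseline wording of the item is likewise not given, and it may differ.

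All of this stands. It removes any claim about direction or magnitude, but it does not give the item a common meaning in both arms. The wording and the timing are fixed in the protocol itself.

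**Conclusion.** The concern holds in a limited form. The care that the item asks about differs by arm, families with no care since discharge have no clear way to answer, and so neither a difference nor the predicted similarity can be cleanly interpreted. The size and sign of any distortion are unknown. The illustrative range is -12.4 to +3.1 points, PRN minus automatic. It assumes attendance as in the bronchiolitis trial, 90% agreement with a visit, 70% to 95% without, and the same rates in both arms. It is not an estimate of bias, and part of any gap may be a true effect.

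Severity is minor. The outcome is exploratory. It is also outside the stated basis for preferring PRN (section 5), which is non-inferiority on readmission with similar safety outcomes. The Table 7 mark is a real but small inconsistency.

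**What to change.** Before the item is used, do one of the following.

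1. Replace it with a single-concept statement that every family can answer whether or not care was received, for example satisfaction with how the child's follow-up has been handled since discharge. Joining two ideas, such as the plan and the help available, would make the answer ambiguous again. Cost: a slightly different construct, which in an unblinded trial may partly reflect approval of the assignment.
2. Keep the item and add a response for no medical care received since discharge. Report that category by arm alongside the others in the full intention-to-treat population. Do not drop those families, since restricting to families who received care selects on something the assignment influences, and do not count them as dissatisfied. Cost: one extra response category and a result with more than two levels.

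In either case, reconcile the while-hospitalized mark in Table 7 with section 8.6 and the item's wording: remove the mark, or state what is asked at that time. This changes one table cell and no analysis.
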